6.2.2 During Treatment

- Adverse events: Diary (on paper or electronic - optional) every week until four weeks after ended treatment
- Registration of concomitant medications
- Blood analyses 2 and 4 weeks after treatment start (Hb, white blood cell count with differential, platelet count, ASAT, ALAT, GT, ALP, Creatinine)
- Talk (meeting or telephone, optional) 1 week after treatment start to uncover reasons for discontinuation of IMP (deterioration, progression or other - see 6.3)
- Non-scheduled visit in case of disease progression SAE or SUSAR
- Cerebral MRI and neuropsychological screening in a subset of patients (see APPENDIX A)

6.2.3 End of Treatment Visit (four weeks after ended treatment)

- Counting and relinquishment of remaining pills
- Collection of patients diary
- Registration of symptoms, concomitant medication, and adverse events
- Composite clinical score
- FSS

6.2.4 Withdrawal Visit (desirable but voluntary)

- Interview about medical history, symptom description, concomitant medication, reason for withdrawal, and adverse events
- Composite clinical score

6.2.5 Six months After End of Treatment (Follow-up)

- Interview about symptom description, concomitant medication, and sick leave attributable to LNB
- Composite clinical score
- FSS, PHQ-15, SF-36
- Laboratory analyses
 - Blood: Hb, white blood cell count with differential, platelet count, ASAT, ALAT, GT, ALP, Creatinine, CRP, electrophoresis, Bb antibodies, TBE antibodies
 - CSF: Cellcount, protein level, Oligoclonal bands, Bb antibodies,
 - In addition aliquots of specimens will be transferred for biobank storage
- Cerebral MRI and neuropsychological testing in a subset of patients (Appendix A)

6.2.6 Twelve months After End of Treatment (Follow-up)

- Interview about symptom description, concomitant medication, and sick leave attributable to LNB
- Composite clinical score
- FSS, PHQ-15
- Laboratory analyses
 - Blood: Hb, white blood cell count with differential, platelet count, ASAT, ALAT, GT, ALP, Creatinine, CRP, electrophoresis, Bb antibodies, TBE antibodies
 - CSF: Cellcount, protein level, Oligoclonal bands, Bb antibodies,
 - In addition aliquots of specimens will be transferred for biobank storage

6.3 Criteria for Patient Discontinuation

Patients may be discontinued from study treatment and assessments at any time. Specific reasons for discontinuing a patient for this study are:

- Voluntary discontinuation by the patient who is at any time free to discontinue his/her participation in the study, without prejudice to further treatment.
- Safety reason as judged by the coordinating investigators
- Major protocol deviation

- Incorrect enrolment ie, the patient does not meet the required inclusion/exclusion criteria for the study
- Patient lost to follow-up
- A female patient becoming pregnant during treatment
- Disease progression
- Deterioration in the patient's condition which in the opinion of the coordinating investigators warrants study medication discontinuation (to be recorded as an AE or under Investigator Discretion)
- Patient's non-compliance to study treatment and/or procedures

6.4 Procedures for Discontinuation

6.4.1 Patient Discontinuation

Patients who withdraw or are withdrawn from the study, will either stop further treatment or receive another antibiotic therapy. If possible, a final assessment shall be made (withdrawal visit and/or follow-up visits). The reason for discontinuation will be recorded, and the investigator will follow up any significant adverse events until the outcome is either recovered or resolved. Patients who withdraw or are withdrawn from the study before start of treatment, will be replaced.

6.4.2 Trial Discontinuation

The whole trial may be discontinued in the event of any of the following:

- Occurrence of AEs unknown to date in respect of their nature, severity and duration
- Medical or ethical reasons affecting the continued performance of the trial
- Difficulties in the recruitment of patients

The coordinating investigators will inform all investigators, the relevant Competent Authorities and Ethics Committees of the termination of the trial along with the reasons for such action. If the study is terminated early on grounds of safety, the Competent Authorities and Ethics Committees will be informed within 15 days.

6.5 Laboratory Tests

Blood and CSF samples will be analyzed at the local laboratories for registration of side effects of treatment and for diagnostic purposes according to existing routines. In addition, aliquots of specimens will be transferred for biobank storage and applied for genetic and immunologic purposes. Details regarding collection, handling, storage, packaging, shipment and destruction will be described in WP3 and WP4 in BorrSci (Appendix A).

7 ASSESSMENTS

7.1 Assessment of Efficacy

The treatment efficacy will be assessed by measuring symptoms and signs six months after ended treatment and summarized on a composite clinical score which reports subjective symptoms and objective findings in a clinical neurological examination. The primary endpoint is improvement in the composite clinical score. The score is a modified version of a score used in an earlier treatment trial in LNB (5). Even if the score is not validated it is, in our opinion, the best way to assess outcome after LNB as it addresses and grades the most commonly reported remaining symptoms and signs. Our experience with the previous score was that it worked well, but some points were not entirely clear or somewhat overlapping. We therefore find it appropriate and more accurate to simplify it to reduce interrater disagreement and scale biases.

To support treatment effect assessment we have chosen several secondary endpoints; inflammatory findings in CSF as measured by cellcount, protein level and oligoclonal bands, fatigue as measured by FSS, burden of somatic symptoms as measured by PHQ-15, and health related quality of life as measured by SF-36. We will also apply proportion of patients with full recovery (score zero on the composite clinical score) as a secondary endpoint. In a subset of patients, MRI findings and neuropsychological profile will be a secondary endpoint.

7.2 Safety and Tolerability Assessments

Significant findings that are present prior to the signing of informed consent will be included in the relevant medical history/ current medical condition page of the CRF. For the assessment of safety and tolerability, refer to Flow chart in Section 6 and Table 3.

8 SAFETY MONITORING AND REPORTING

The site investigators and the coordinating investigators are responsible for the detection and documentation of events meeting the criteria and definition of an adverse event (AE) or serious adverse event (SAE). Each patient will be instructed to contact the site investigator immediately should they manifest any signs or symptoms they perceive as serious.

8.1 Definitions

8.1.1 Adverse Event (AE)

An AE is any untoward medical occurrence in a patient administered a pharmaceutical product and which does not necessarily have a causal relationship with this treatment. The term AE is used to include both serious and non-serious AEs. An AE can be any unfavorable and unintended sign (including an abnormal laboratory finding), symptom, or disease temporally associated with the use of a medicinal (investigational) product, whether or not related to the medicinal (investigational) product.

8.1.2 Serious Adverse Event (SAE)

Any untoward medical occurrence that at any dose:

- Results in death
- Is immediately life-threatening
- Requires in-patient hospitalization or prolongation of existing hospitalization
- Results in persistent or significant disability or incapacity
- Is a congenital abnormality or birth defect
- Is an important medical event that may jeopardize the subject or may require medical intervention to prevent one of the outcomes listed above

Medical and scientific judgment is to be exercised in deciding on the seriousness of a case. Important medical events may not be immediately life threatening or result in death or hospitalization, but may jeopardize the subject or may require intervention to prevent one of the listed outcomes in the definitions above. In such situations, or in doubtful cases, the case should be considered as serious. Hospitalization for administrative reason (for observation or social reasons) is allowed at the investigator's discretion, and will not qualify as serious unless there is an associated adverse event warranting hospitalization.

8.1.1 Suspected Unexpected Serious Adverse Reaction (SUSAR)

Adverse Reaction: all untoward and unintended responses to an investigational medicinal product related to any dose administered.

Unexpected Adverse Reaction: an adverse reaction, the nature or severity of which is not consistent with the applicable product information.

Suspected Unexpected Serious Adverse Reaction: SAE (see section 8.1.2) that is unexpected as defined in section 8.2 and possibly related to the IMP.

8.2 Expected Adverse Events

Nausea, vomiting, diarrhea, vaginitis, skin reactions, disturbances in bloodtests are all expected AE. The manufacturers SmPC will be used as reference document. All AE will be recorded in the CRF.

8.3 Disease Progression

Disease progression in this trial is defined as worsening of the patient's condition attributable to LNB despite treatment for 14 days with doxycycline, or serious progression of neurological signs from CNS (myelitis or encephalitis) during treatment. Events that are definitely due to disease progression will not be reported as an AE/SAE unless the investigator considers there is a causal relationship between treatment with IMP or protocol design/procedures and the disease progression/recurrence. Death due to progressive disease is to be recorded on a specific from in the CRF but not as an SAE.

8.4 Time Period for Reporting AE and SAE

For each patient the standard time period for collecting and recording AE and SAEs will begin at start of study treatment and will continue for at least four weeks following the last dose of study treatment for each patient.

During the course of the study all AEs and SAEs will be proactively followed up for each patient; events should be followed up to resolution, unless the event is considered by the investigator to be unlikely to resolve due to the underlying

disease. Every effort should be made to obtain a resolution for all events, even if the events continue after discontinuation/study completion.

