Centers:	Sørlandet Hospital + 5-10 other Norwegian hospitals
Study Period:	Estimated date of first patient enrolled: 01.10.15 Anticipated recruitment period: 01.10.15- 31.12.19 Estimated date of last patient completed: 31.12.20
Treatment Duration:	Six weeks
Follow-up:	13 months
Objectives	
Primary objective
 
To answer the question “is two weeks doxycycline treatment (currently suggested treatment) at least as effective as six weeks doxycycline treatment in Lyme Neuroborreliosis?”
 
Key secondary objectives
 
To provide a better understanding of the pathogenesis and long-term complaints, and to search for new biomarkers in LNB
 
To collect clinical data, blood, and CSF in a biobank for future research

Endpoints:	
Primary endpoint:
 
Improvement in composite clinical score defined as clinical score at inclusion minus clinical score at 6 months.
 
Secondary endpoints:
 
Fatigue Severity Scale (FSS) Patient Health Questionnaire (PHQ-15) Short Form 36 (SF-36) Blood and CSF findings MRI, and neuropsychological assessments in a subset of patients Adverse events

Study Design:	Multicenter, non-inferiority, randomized, penta-blind, placebo-controlled trial
Main Inclusion Criteria:	
1. Neurological symptoms suggestive of LNB without other obvious reasons and one or both of
a. Cerebrospinal fluid pleocytosis (≥ 5 leukocytes/mm³)b. Intrathecal Bb antibody production2. Signed informed consent
Main Exclusion Criteria	
- Age less than 18 years- Pregnancy, breast-feeding- Adverse reaction to tetracyclines- Treatment with cephalosporin, penicillin, or tetracycline the last 14 days- Serious liver or kidney disease that contraindicates use of doxycycline- Lactose intolerance- Need to use medications contraindicated according to SmPC of the IMP
Sample Size:	120 patients
Efficacy Assessments:	Comparison of clinical outcome six months after end of treatment between the two treatment groups.
Safety Assessments:	Subjective experiences and blood tests including hematology and biochemistry for four weeks after ended treatment.

TABLE OF CONTENTS

CONTACT DETAILS.....	2
SIGNATURE PAGE	3
PROTOCOL SYNOPSIS.....	4
TABLE OF CONTENTS	5
LIST OF ABBREVIATIONS AND DEFINITIONS OF TERMS.....	8
1 INTRODUCTION.....	9
1.1 Background – Lyme Neuroborreliosis (LNB).....	9
1.2 Background - Therapeutic Information.....	9

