2.2 Secondary Endpoints

Improvement of composite clinical score from inclusion to 12 months after end of treatment defined as clinical score at inclusion minus clinical score at 12 months. (Table1)

Fatigue Severity Scale (FSS) at six and 12 months after end of treatment. FSS is translated and validated for Norwegian purposes (12). It measures level of agreement (1– 7) with nine statements. The final score represents the mean value of the nine items. Severe fatigue is defined as a score >5 in a Norwegian population. Reported mean score in 20 American

healthy adults is 2.3 (13), and reported mean score in 50 Norwegian patients treated for LNB is 3.5 versus 2.1 in the control group (3).

Patient Health Questionnaire (PHQ-15) at six months. PHQ-15 is a brief, validated questionnaire, which consists of 13 questions concerning severity of different subjective somatic symptoms the last 4 weeks, and 2 questions concerning sleep and tiredness. Each item is scored from 0 to 2, and sum score ranges from 0 to 30. Sum scores of 5, 10, and 15 represent cutpoints for low, medium, and high symptom severity, respectively (27).

Short Form-36 (SF-36): SF-36 is a valid and reliable questionnaire assessing health related quality of life. It consists of 36 questions concerning general health perceptions, physical functioning, physical role functioning, emotional role functioning, social role functioning, bodily pain, vitality and mental health. A Norwegian normal material exist (28).

CSF findings at six and 12 months: Cell count, IgG index, OCB's, and *Bb* antibodies

Other laboratory tests, MRI, and neuropsychological assessments: In a subset of patients at inclusion and six months after end of treatment (WP4 of BorrSci).

Safety as measured by serious adverse events and less serious side effects of treatment (Table 3)

Table 3. Safety measures

Treatmentweek	0	1	2	3	4	5	6	7-10
Nausea		x	x	x	x	x	x	x
Vomiting		x	x	x	x	x	x	x
Diarrhea		x	x	x	x	x	x	x
Skin reactions		x	x	x	x	x	x	x
Vaginitis		x	x	x	x	x	x	x
Blodtests (Hb, Hb, white blood cell count with differential, platelet count, ASAT, ALAT, GT, ALP, Creatinine)	x		x		x			
Other AE or complications		x	x	x	x	x	x	x

Secondary and exploratory objectives and their endpoints and assessments are detailed in WP 3 and 4 (Appendix A)

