8.5 Recording of Adverse Events

If the patient has experienced adverse event(s), the investigator will record the following information in the CRF:

- The nature of the event(s) will be described by the investigator in precise standard medical terminology (i.e. not necessarily the exact words used by the patient).
- The duration of the event will be described in terms of event onset date and event ended data.
- The intensity of the adverse event: Mild/Moderate/Severe according to Common Terminology Criteria for Adverse Events version 4.0 (CTCAE).
- The Causal relationship of the event to the study medication will be assessed as one of the following:

Unrelated:

There is not a temporal relationship to investigational product administration (too early, or late, or investigational product not taken), or there is a reasonable causal relationship between non-investigational product, concurrent disease, or circumstance and the AE.

Unlikely:

There is a temporal relationship to investigational product administration, but there is not a reasonable causal relationship between the investigational product and the AE.

Possible:

There is reasonable causal relationship between the investigational product and the AE. Dechallenge information is lacking or unclear.

Probable:

There is a reasonable causal relationship between the investigational product and the AE. The event responds to dechallenge. Rechallenge is not required.

Definite:

There is a reasonable causal relationship between the investigational product and the AE.

- Action taken
- The outcome of the adverse event – whether the event is resolved or still ongoing.

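### Adverse-event recording is required only to about week 10, so harms of the lumbar punctures scheduled at 6 and 12 months are not systematically collected or identifiable as procedure-related

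*Combined protocol and SAP*

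**What the plan says.** **The recording window.** Section 8.4 starts AE and SAE recording at the start of study treatment; it "will continue for at least four weeks following the last dose of study treatment for each patient". The synopsis describes safety assessment as "Subjective experiences and blood tests including hematology and biochemistry for four weeks after ended treatment". The AE diary in 6.2.2 runs "every week until four weeks after ended treatment", and the last column of Table 3 is weeks 7-10. The last routine visit with an AE item is the End of Treatment visit (6.2.3), four weeks after treatment: "Registration of symptoms, concomitant medication, and adverse events".

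**The later punctures.** Section 2.2 lists among the secondary endpoints "CSF findings at six and 12 months: Cell count, IgG index, OCB's, and *Bb* antibodies". The flow chart, 6.2.5 and 6.2.6 schedule CSF sampling at both visits. The flow chart marks MRI and neuropsychology as subset procedures but does not mark CSF sampling that way. Its footnote says that the baseline sample was obtained by the clinician before inclusion, so the two follow-up punctures are the ones the trial adds.

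**What the later visits ask.** The interview item in 6.2.5, repeated in 6.2.6, is "Interview about symptom description, concomitant medication, and sick leave attributable to LNB". Neither list, nor the flow chart at these visits, has an adverse-event entry.

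**How causality is graded.** Section 8.5 states: "The Causal relationship of the event to the study medication will be assessed", on a scale from unrelated to definite. No category or field covers study procedures. Section 8.3 does mention a "causal relationship between treatment with IMP or protocol design/procedures", but only when deciding whether disease progression must be reported as an event.

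**The concern.** A lumbar puncture is invasive, and here it is repeated twice in every patient for trial purposes. The AE window is built around the drug and has closed months before either puncture. The protocol names adverse events explicitly at the End of Treatment and Withdrawal visits, so their absence from the 6- and 12-month lists reads as a real limit on what is collected.

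The stake is the safety account. Annual safety reports (8.6.3) and the safety part of the Clinical Study Report (8.6.4) could not tell an absence of puncture-related harm from an absence of questions about it. The risk discussion in section 1.4 names drug effects and antibiotic resistance but not the punctures, so nothing there prompts sites to look for such events.

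**Working it through.** No power, margin or variance calculation is involved. The check is calendar arithmetic, a count, and a trace of how an event would be handled.

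**Inputs**
- Treatment lasts 6 weeks (5.3).
- Required recording runs to at least 4 weeks after the last dose (8.4).
- CSF sampling takes place 6 and 12 months after end of treatment (2.2, flow chart, 6.2.5, 6.2.6).
- Planned enrolment is 120 (4.2).
- Conversion used: 6 months = 26 weeks, 12 months = 52 weeks.

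**Step 1: reproduce the plan's figure.** Week 6 + 4 = week 10. This agrees with the end-of-week-10 column in the flow chart and with the last column of Table 3.

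**Step 2: timing of the punctures.**
- First: 6 + 26 = week 32, which is 32 - 10 = 22 weeks after the last scheduled AE question.
- Second: 6 + 52 = week 58, which is 58 - 10 = 48 weeks after it.
- Planned AE collection covers 10 of 58 weeks, 10 / 58 = 17% of the time from start of treatment to the last visit.

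**Step 3: number of procedures.** 120 x 2 = 240. This is a ceiling that assumes every patient attends and is sampled at both visits. The documents give no expected attendance. If both visits were attended at the rate at which 12-month scores were available in the former trial (93 of 102, section 10.1), the count would be 240 x 93 / 102 = 219, and lower if some attending patients decline the puncture. All of them lie outside scheduled AE collection. The documents give no complication rate for lumbar puncture, so no expected number of events is calculated.

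**Step 4: trace an event through the plan.**
- *Hospital admission after the 6-month puncture.* It meets the hospitalisation criterion in 8.1.2. The required window in 8.4 has closed. The site may learn of it if the patient calls (section 8), and 8.6.1 then has it reported within 24 hours. In 8.5 it would probably be graded unrelated to the drug, because of its timing or another circumstance, and nothing in the causality field links it to the puncture.
- *Non-serious complaint after the 6-month puncture.* No AE question follows. The 12-month interview may bring it up as a symptom, but that visit has no AE entry.
- *Any event after the 12-month puncture.* No later visit or contact is scheduled. Only self-report remains.

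**The case against.** The strongest reply is that the plan does not shut these events out. Section 8.4 sets a minimum, so later recording is allowed. Section 8 tells patients to contact the site at once about anything they perceive as serious, and 8.6.1 requires SAE reporting within 24 hours of site knowledge; neither passage gives an end date. The voluntary withdrawal visit also asks about adverse events. All of this stands. A reader might infer that no puncture harm can reach the record, or that the punctures have no safety monitoring at all. The documents do not support either. What remains is that these routes are passive or apply to few patients, depend on what the patient regards as serious, and leave non-serious harm without a scheduled question. The commitment in 8.4 to proactive follow-up concerns carrying events to resolution; it sets no later point for asking about new ones.

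A reader might also infer that 8.5 has nowhere to put such an event. It does: the unrelated category can hold it. The gap is narrower, in that the procedure is not flagged as the cause.

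A third tempting reading is that post-puncture headache or back pain contaminates the primary endpoint. Table 2 counts only symptoms related to the LNB, both visit lists place the composite score ahead of the laboratory sampling, and both arms have the same punctures under blinding. Misattribution by a patient is possible and the order is not stated, but no between-arm bias is shown.

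It is also fair that a four-week window suits the drug comparison, which is the trial's main safety question. Finally, specimen-collection details are deferred to Appendix A, and the consent form is Appendix D. Neither was available for this review, so a provision for puncture events could exist there.

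**Conclusion.** The point holds as a gap in systematic collection. Following the plan as written, up to 240 trial-scheduled lumbar punctures take place 22 or 48 weeks after the last scheduled AE question, at visits with no AE item and with causality graded only against the drug. Their harms would be recorded incompletely, and those recorded could not be separated as procedure-related. Serious events may still surface through self-report and SAE reporting.

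The conclusion rests on the visit lists, flow chart and section 8 as they stand, on full attendance for the figure of 240, and on Appendix A containing no separate provision. It does not depend on any assumed complication rate. Neither the randomised efficacy comparison nor the drug-safety comparison is affected. This is a worthwhile, inexpensive improvement to the safety plan.

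**What to change.** 1. **Section 8.4:** extend SAE and procedure-related AE recording to a fixed, short, stated period after each follow-up lumbar puncture. The drug-related window can stay as it is.
2. **Sections 6.2.5 and 6.2.6 and the flow chart:** add an AE/SAE line at both visits. At 12 months, ask explicitly about the period after the six-month puncture.
3. **After the 12-month puncture:** capture events by one brief telephone contact or by an instruction to the patient to report back, since no later visit exists.
4. **Section 8.5:** add a field for relation to a study procedure, separate from relation to study medication.
5. **Minor precaution:** state in 6.2.5 and 6.2.6 that the composite score is completed before the puncture.

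If Appendix A already covers events after the punctures, a cross-reference from 8.4 would meet part of this.

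The cost is protocol wording, one or two eCRF fields and one short contact per patient; the rest uses existing visits. Treatment, endpoints and sample size do not change.
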